#### 8.1. Primary Effectiveness Analysis

Poolability analysis for study sites will be performed before the main analysis. If sites do have an effect on primary outcome, then site as covariate will be included in main model for primary analysis.

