9.3.3. Unblinding Procedures

Unblinding in case of medical emergency is not applicable since the TI, who is in charge of safety follow-up of subjects, will be aware of the treatment administered.

Overall unblinding will take place at the end of the study only after database lock has occurred.

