11. STATISTICAL METHODS

This section presents a summary of the planned statistical analyses. A statistical analysis plan (SAP) that describes the details of the analyses to be conducted will be written prior to database lock. The SAP will be submitted to the FDA during the course of the study.

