### List of Tables and Figures

#### 1. Introduction

This statistical analysis plan (SAP) describes the planned analysis and reporting for

Multicenter, Prospective Clinical Study to Evaluate Safety and Effectiveness of RHA® 3 versus for Lip Augmentation), dated 22-MAR-2021 version # . The reference document for this SAP is the protocol. Operational aspects related to collection and timing of planned clinical assessments are not repeated in this SAP unless relevant to the planned analysis.

The structure and content of this SAP provide sufficient detail to meet the requirements identified by the Food and Drug Administration (FDA), and International Conference on Harmonization (ICH) of Technical Requirements for Registration of Pharmaceuticals for Human Use: Guidance on Statistical Principles in Clinical Trials. All work planned and reported for this SAP will follow internationally accepted guidelines, published by the American Statistical Association and the Royal Statistical Society, for statistical practice.

The planned analyses identified in this SAP may be included in clinical study reports (CSRs), regulatory submissions, or future manuscripts. Also, post-hoc exploratory analyses not necessarily identified in this SAP may be performed to further examine study data. Any post-hoc or unplanned, exploratory analysis performed will be clearly identified as such in the final CSR.

The statistical plan described hereafter is an *a priori* plan. It will be submitted to file prior to any unblinded inferential or descriptive analysis of data pertaining

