#### 8. Effectiveness Analysis

The primary and secondary effectiveness analyses will be based on the mITT population. The analyses will be repeated for the PP population.

For categorical variables, the 2 groups will be compared using independent-testing based on a 2-group, 2-sided, Fisher's exact test. For continuous variables, ANCOVA or applicable non-parametric method will be used.

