#### Non-inferiority Analysis (Main Analysis):

To demonstrate non-inferiority of RHA® 3 compared to **reaction of** at 12 weeks after the last treatment, the difference in the TLFS grade change between Baseline and 12 weeks will then be tested between groups (RHA® 3 minus **reaction**).

Normality, homogeneity of variance and random independent samples are required for performing the analysis.

Page 32 of 53

If non-inferiority is achieved, the TLFS grade difference as rated by the BLE at 12 weeks after Baseline will be analyzed in terms of superiority.

A 2-sided 95% CI, based on an analysis such as **sector and the sector and sec** 

- If the lower bound of the CI is >-0.5, then non-inferiority is demonstrated.
- Else, if the lower bound is ≤-0.5, non-inferiority is not demonstrated.
- If the lower bound of the CI is ≥0.5, then RHA® 3 superiority is demonstrated.

Page 33 of 53

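### Does letting the 12-week outcome data decide whether site enters the primary model undermine the non-inferiority test in SAP 8.1?

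*SAP*

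**What the plan says.** SAP 8.1 (Primary Effectiveness Analysis) opens with the site check: "Poolability analysis for study sites will be performed before the main analysis". It then makes the model conditional on the result: "If sites do have an effect on primary outcome, then site as covariate will be included in main model for primary analysis". The primary outcome is the blinded evaluator's change in Teoxane Lip Fullness Scale (TLFS) grade from Baseline to 12 weeks after the last treatment (SAP 2.2.1.1).

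The decision rule follows under the Non-inferiority Analysis heading: "If the lower bound of the CI is >-0.5, then non-inferiority is demonstrated". The interval is introduced with "A 2-sided 95% CI, based on an analysis such as", after which the name of the analysis is blacked out. SAP 8 gives the general method: "For continuous variables, ANCOVA or applicable non-parametric method will be used".

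On timing, SAP 1 says of the plan: "It will be submitted to file prior to any unblinded inferential or descriptive analysis of data pertaining" (the visible sentence breaks off there). Protocol 11 adds: "The SAP will be submitted to the FDA during the course of the study". Protocol 9.3.3 says: "Overall unblinding will take place at the end of the study only after database lock has occurred".

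**The concern.** A primary model should normally be fixed before anyone sees the endpoint. Here a preliminary look at the endpoint decides whether site is in the model, and the lower bound from that model is read against -0.5. The visible text names no test or threshold for an effect of site. It does not say that the check is run without treatment codes, and it does not show whether randomization is stratified by site.

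Three things could be at stake:

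- the false-positive rate of the non-inferiority claim;
- the coverage of an interval that ignores the preliminary test;
- a borderline verdict that depends on which model the test happened to pick.

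**Working it through.** **Inputs from the documents.** There are 200 to 202 subjects (Protocol 7.2) randomized 3:1 (Protocol 9.2), so about 150 versus 50. There are 7 to 10 sites (Protocol 7.3). The margin is -0.5 with a two-sided 95% interval (SAP 8.1), so the one-sided level is 0.025.

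**Assumed, because not visible.** Residual SD is 0.8 or 1.0 and between-site SD is 0, 0.2 or 0.4. When sites differ, their share of variance runs from 0.2²/(0.2² + 1.0²) = 3.8% to 0.4²/(0.4² + 0.8²) = 20%. Site is kept if its F-test gives p < 0.05. Randomization is taken both with and without stratification by site.

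**The plan's own figure.** The inputs to the sample size are blacked out, so it cannot be reproduced. For orientation, SE = SD × √(1/150 + 1/50) = 0.1633 × SD. At a true difference of 0, power is Φ(0.5/SE − 1.96), which gives 96.9% at SD 0.8 and 86.5% at SD 1.0.

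**Why little error is expected.** Allocation does not depend on site, so the treatment difference is estimated without bias with or without the site term. The preliminary test looks at differences between sites, and its result dictates the model. Nobody picks the more favourable lower bound.

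**Simulation.** Each scenario had 200 subjects and an analysis of covariance with baseline grade. There were 4,000 trials at a true difference of -0.5, with simulation error √(0.025 × 0.975/4000) ≈ 0.25 points, and 2,000 trials at a true difference of 0. Cells give % for never site / always site / SAP rule.

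| Stratified by site | Sites | Between-site SD | Residual SD | Site enters under rule | Type I error | Power at 0 |
|---|---|---|---|---|---|---|
| No | 10 | 0 | 1.0 | 4.65% | 2.68 / 2.58 / 2.72 | 85.9 / 84.2 / 85.8 |
| No | 7 | 0.2 | 1.0 | 38.45% | 2.28 / 2.25 / 2.35 | 84.2 / 84.5 / 84.8 |
| No | 10 | 0.4 | 1.0 | 86.52% | 2.28 / 2.35 / 2.35 | 79.95 / 83.15 / 83.35 |
| Yes | 7 | 0.2 | 0.8 | 55.65% | 2.28 / 2.28 / 2.38 | 96.45 / 97.1 / 97.05 |
| Yes | 10 | 0.4 | 0.8 | 95.18% | 1.75 / 2.58 / 2.58 | 94.65 / 96.3 / 96.3 |

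Across all scenarios type I error was 1.9% to 3.0% under the rule and 1.9% to 3.0% with site always in. The largest difference within a scenario was about 0.2 points. Where sites differ strongly the rule nearly always brings site in and recovers the power that the model without site loses. A separate simulation (8 to 10 sites, SD 0.8 to 1, site share 0 to 10%) gave 2.3% to 2.6% under the rule and 2.3% to 2.5% with site always in.

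**Cost of always including site when sites do not differ.** Without stratification, K sites take up on average (K − 1)/(N − 1) of the treatment contrast, so the SE grows by the factor 1/√(1 − (K − 1)/199).

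- K = 7: 1/√(1 − 6/199) = 1.015, or 1.5% wider.
- K = 10: 1/√(1 − 9/199) = 1.023, or 2.3% wider (2.4% in simulation).
- At SD 1.0 and K = 10, SE is 0.1633 × 1.023 = 0.1671 and power is Φ(0.5/0.1671 − 1.96) = 84.9%. That is 1.6 points below 86.5% and agrees with the first row of the table.

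**The case for a change.** The strongest case for the concern is that the dependence is real. No visible sentence removes it, and a blacked-out threshold would define the condition without abolishing it. Fixing the site term would take one sentence and a rule for small sites. The rule and an always-site model can also reach different verdicts. With a site effect present (share 3% to 10%) and no stratification, they differed in 0.05% to 4.2% of simulated trials; with stratification, in 0% to 0.95%. With no site effect and no stratification the range was 0.3% to 5.9%, and 6.3% in one further cell.

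The dependence stands as a description of the text, but these figures do not show harm. The disagreements run in both directions. The net difference in pass rate, rule minus always-site, is -0.2 to +0.9 points unstratified and -0.3 to +0.1 stratified. The large figures come from borderline settings. In one such setting (SD 1, true difference -0.15, 5% site share) verdicts differ in 3.15% of trials while power is 57.9% against 57.0%. At a true difference of 0, SD 0.7 to 0.8 and a site effect present, the range is 0.05% to 0.6%. The highest rates occur when sites do not differ at all, where adjustment only adds noise.

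Without stratification the interval after the preliminary test is very slightly too narrow. Coverage is 0.13 to 0.19 points lower in one set of runs and differs by at most about 0.3 points in another. With stratification the effect disappears. A free choice of the better model would raise type I error to between 2.0% and 3.6%, but SAP 8.1 does not permit that choice.

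Fixing the site term would also not leave a single analysis untouched by the data. SAP 8 would still allow a non-parametric method in place of covariance analysis, and SAP 8.1 lists normality and equal variance as requirements. The unnamed test and threshold cannot count against the plan, because text around SAP 8.1 is blacked out.

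**Conclusion.** The concern does not hold. The site rule depends on outcome data, but it is set in advance and says what follows from a site effect. In every scenario checked it controls type I error as well as a fixed site term does, to within about 0.2 points. Its power is within about 0.5 point of the fixed term when sites differ, and up to about 1.6 points higher when they do not. A fixed site term is a respectable alternative, and some statisticians would prefer it, but it exchanges one valid model for another.

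This conclusion assumes a residual SD near 0.8 to 1.0, up to about 20% of variance between sites, a 0.05 threshold and no treatment-by-site interaction, which was not simulated. The re-run in the table treats the graded scale as continuous. The visible text does not say whether the site check is run without treatment codes. In simulation, a check that ignored treatment chose the same model in 97% to 99.8% of trials, so little turns on that.

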#### Non-inferiority Analysis (Main Analysis):

To demonstrate non-inferiority of RHA® 3 compared to **reaction of** at 12 weeks after the last treatment, the difference in the TLFS grade change between Baseline and 12 weeks will then be tested between groups (RHA® 3 minus **reaction**).

Normality, homogeneity of variance and random independent samples are required for performing the analysis.

Page 32 of 53

If non-inferiority is achieved, the TLFS grade difference as rated by the BLE at 12 weeks after Baseline will be analyzed in terms of superiority.

A 2-sided 95% CI, based on an analysis such as **sector and the sector and sec** 

- If the lower bound of the CI is >-0.5, then non-inferiority is demonstrated.
- Else, if the lower bound is ≤-0.5, non-inferiority is not demonstrated.
- If the lower bound of the CI is ≥0.5, then RHA® 3 superiority is demonstrated.

Page 33 of 53

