12 weeks 24 after the last treatment, and 4 weeks (24 after retreatment or until all treatment-related ongoing AEs have resolved or resolved with sequelae as per TI judgment or if follow-up is no longer possible.

A follow-up telephone call for safety will be performed at 3 days after each treatment (initial, touch-up, and retreatment, respectively). Subjects will report their CTRs in a subject diary for days after each injection. The diary will also include a list of selected AEs potentially associated with injection of dermal fillers for subjects to report if applicable. Confidential
Clinical Investigation Plan

Subjects who had entered the study under earlier versions of the CIP (version and earlier) and who do not agree with the extension of their participation in the study, to 52 weeks after last treatment, will be allowed to continue with the visits as originally planned (see Table 2-2). They will exit the study **1000** 36 weeks after last treatment) or, if they receive retreatment **1000** they will have a follow-up telephone call **1000** and will exit the study **1000** 4 weeks after retreatment.

A BLE will conduct assessments of effectiveness during the study, including assessment of the primary endpoint at Visit 4 (12 weeks after the last treatment). The BLE will conduct effectiveness evaluations

Page 46 of 132

Clinical Investigation Plan

Confidential

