8.1.3. Visit (4 Weeks After the Initial Treatment)

Visit is performed at the site 4 weeks \pm 3 days after the initial treatment.

If deemed necessary by the TI, an optional touch-up treatment can be administered at this visit. The touch-up treatment will be performed either with RHA[®] 3 or depending on the treatment allocation at Visit 1.

Page 57 of 132

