#### 1.2. Hypothesis

The Teoxane Lip Fullness Scale (TLFS) change from Baseline for subjects treated with RHA® 3 will be statistically non-inferior to the change from Baseline for subjects treated with for the assessment of lip augmentation and fullness as determined by the Blinded Live Evaluator (BLE) using the TLFS at Week 12 after the last treatment (initial or touch-up).

Page 5 of 53

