#### 2.1.1. Primary Objective

To assess the effectiveness (non-inferiority) of RHA® 3 versus **presented** on adding volume and fullness to the lips in subjects seeking lip augmentation, 12 weeks after the last treatment (initial or touch-up).

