#### 2.2.1.2. Secondary Effectiveness Endpoints

The secondary effectiveness endpoints are:

- TLFS change from Baseline assessed:

   By the BLE at each visit at the study from Visit 4
- Responder rate calculated using TLFS assessed:
   O By the BLE at each visit at the study from Visit 4

A responder will be defined as a subject who has a  $\geq 1$  grade improvement on the TLFS.

• Subject satisfaction using the Subject Satisfaction Scale at each visit at the study site starting at Visit 2

FACE-Q scores for each module (satisfaction with lips and satisfaction with outcome) assessed by the subject at each visit

- GAIS as assessed:
  - o By the BLE starting at each visit at the study from Visit 4

Statistical Analysis Plan Protocol Number	

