#### 6.1.6.1. Responder Rate

Definition of responder: ≥1-grade point on the TLFS 12 weeks after the last treatment when compared to pretreatment (Baseline). A positive change from Baseline value is considered as improvement.

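### SAP 8.1 times the follow-on superiority analysis from Baseline, whereas the primary endpoint is timed from the last treatment; the two differ for subjects who have a touch-up

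*SAP*

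**What the plan says.** Under the main-analysis heading in SAP 8.1, the non-inferiority test is placed "at 12 weeks after the last treatment, the difference in the TLFS grade change". A few lines later, if non-inferiority is achieved, "the TLFS grade difference as rated by the BLE at 12 weeks after Baseline will be analyzed in terms of superiority". One 2-sided 95% confidence interval is then described, and all the decision bullets refer to it.

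The other visible full statements of the primary time point count from the last treatment:

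- SAP 1.2 (Hypothesis): "using the TLFS at Week 12 after the last treatment (initial or touch-up".
- SAP 2.1.1 (Primary Objective): "12 weeks after the last treatment (initial or touch-up".
- SAP 2.2.1.1 (Primary Effectiveness Endpoint): 12 weeks after the last day of treatment.
- SAP 6.1.6.1 (Responder Rate): "12 weeks after the last treatment when compared to pretreatment (Baseline".
- Protocol 7: "primary endpoint at Visit 4 (12 weeks after the last treatment".
- Protocol 8.1.7: the primary endpoint visit is scheduled 12 weeks after the initial or touch-up treatment, whichever was last.

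SAP 6.1.1 defines Baseline as the last non-missing observation before the first study treatment. Protocol 8.1.3 places a site visit 4 weeks ± 3 days after the initial treatment and says that "an optional touch-up treatment can be administered at this visit".

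**The concern.** Baseline and last treatment are the same anchor only for subjects who receive no touch-up. For the others they lie about 4 weeks apart. Taken literally, the superiority sentence would compare groups at about 8 weeks since last treatment for touch-up subjects and 12 weeks for the rest. It would also rest on different data from the non-inferiority test on which it depends.

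The SAP describes itself as an a priori plan, and this is the visible rule from which a superiority statement would follow. A rule that names a time point at odds with the endpoint invites a question later about which rating was planned.

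**Working it through.** The documents give no figure of their own for this gap, so it is built from their stated intervals.

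**Inputs**

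- Baseline and initial treatment both fall at Visit 1, taken as day 0 (Protocol 9.5 and 9.6; SAP 6.1.1).
- Touch-up, if given: 4 weeks ± 3 days after the initial treatment, i.e. day 28 ± 3 = day 25 to 31 (Protocol 8.1.3; SAP 3.1 gives 4 weeks).
- 12 weeks = 84 days. No window for the 12-week visit is visible, so none is applied.

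**Step 1: day of the primary visit = day of last treatment + 84**

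- No touch-up: 0 + 84 = day 84.
- Touch-up: 25 + 84 = day 109 to 31 + 84 = day 115, which is 15.6 to 16.4 weeks after Baseline.

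**Step 2: time since last treatment at 12 weeks after Baseline = 84 − day of last treatment**

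- No touch-up: 84 − 0 = 84 days (12 weeks).
- Touch-up: 84 − 31 = 53 days to 84 − 25 = 59 days, which is 7.6 to 8.4 weeks.

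| | No touch-up | Touch-up |
|---|---|---|
| Primary visit, days after Baseline | 84 | 109 to 115 |
| Days since last treatment at the primary visit | 84 | 84 |
| Days since last treatment at 12 weeks after Baseline | 84 | 53 to 59 |

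**Step 3: is there a rating at 12 weeks after Baseline for touch-up subjects?**

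SAP 2.2.1.2 lists the post-treatment TLFS change and responder ratings as "By the BLE at each visit at the study from Visit 4". Protocol 7 identifies Visit 4 as the visit 12 weeks after the last treatment. For touch-up subjects the visible site visits up to that point are at about week 4 (the touch-up visit), about week 8 (4 weeks after touch-up) and about week 16 (Visit 4). None is at week 12, and the blinded evaluator's post-treatment ratings start only at Visit 4. Much of the schedule is redacted, so this is a statement about the visible text.

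**Step 4: which time will the analysis use?**

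SAP 6.1.4 bases analyses on the scheduled visit recorded in the eCRF, without realignment. SAP 8.1 describes a single interval that serves both the non-inferiority and the superiority bullets. Both point to Visit 4.

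**The case against.** The strongest reply is that this slip cannot change a result. Analyses follow scheduled visits, the blinded evaluator's visible ratings begin at Visit 4, and one interval feeds every decision bullet. On the visible text, the literal instruction cannot be carried out for touch-up subjects. The phrase also has a plausible origin: both documents often shorten the endpoint to a change between Baseline and 12 weeks, with the last-treatment anchor stated nearby, and the superiority sentence looks like a garbled form of that shorthand.

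All of this stands as evidence of intent, and it keeps the point minor. It does not make the sentence correct. The sentence is unredacted, operative text that names a different anchor from the endpoint it analyses.

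Two stronger readings are tempting, and the documents support neither.

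- A reader might infer that the two tests will in fact use different data, and that a countable share of the 200 subjects is affected. The touch-up share is not given in the visible text, and the scheduled-visit rule points to Visit 4 for everyone. No count of affected subjects can be defended.
- A reader might also take the third decision bullet, which declares superiority only at a lower bound of 0.5 or more, as a second error. The rule is explicit, stricter than a bound above 0, and may be deliberate. Text directly above the bullets is redacted, so a label or rationale cannot be called missing. It does not affect the non-inferiority test.

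**Conclusion.** The contradiction is real. The superiority sentence in SAP 8.1 conflicts with the opening of its own section, with SAP 1.2, 2.1.1 and 2.2.1.1, and with Protocol 7 and 8.1.7. For touch-up subjects it shifts the stated assessment from 84 days to 53 to 59 days after the last treatment; for other subjects it changes nothing.

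The day counts rest on the ± 3-day touch-up window and on a 12-week visit taken without a window. The effect on the estimated difference cannot be sized. It is probably small, because Visit 4 is almost certainly what will be analysed. Any consequence is limited to a conditional step outside the primary hypothesis. Severity is minor. Confidence is high that the wording is inconsistent, but this does not extend to any consequence for the results.

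**What to change.** Before unblinding, change one phrase in the superiority sentence of SAP 8.1: replace *12 weeks after Baseline* with *12 weeks after the last treatment (initial or touch-up)*, the anchor already used in SAP 1.2 and 2.1.1. Non-inferiority and superiority then refer to the same Visit 4 ratings and the same confidence interval.

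The cost is a one-phrase SAP correction. It needs no extra data or visits and leaves the type I error and the primary test unchanged.

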#### 8.3. Secondary Effectiveness Analysis

#### 8.3.1. TLFS Assessed by BLE

Summary statistics (mean, minimum, maximum, SD, and 95% CI of the mean, change from Baseline) will be provided/presented for each study visit for TLFS grade overall

The following categories are used:

- Grade 1 Very Thin
- Grade 2 Thin
- Grade 3 Moderate
- Grade 4 Full
- Grade 5 Very Full

#### 8.3.2. Responder Rate Based on TLFS

Responder rate will be tabulated by treatment group: frequency of responders, percentage of responders along with 95% CI will be tabulated. Fisher's exact test will be performed to compare responder rates at each applicable visit.

The following categories are used:

- Responder
- Non-responder.

Page 34 of 53

GAIS grade frequencies and percentages will be calculated and presented for each study visit.

The GAIS is a subjective 5-grade dynamic scale as detailed below, will be assessed by Investigators and subjects.

Grade description:

- 1. Much improved
- 2. Improved
- 3. No change
- 4. Worse
- 5. Much worse

,		
	the second s	

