6.2.4. Safety Objective

• To assess the safety of RHA[®] 3 in subjects after lip augmentation

Confidential

	Objectives	Endpoints
Pr	imary effectiveness	
•	To assess the effectiveness (non- inferiority) of RHA [®] 3 versus control of the set of	 The effectiveness of RHA[®] 3 will be demonstrated if the change from Baseline for subjects treated with RHA[®] 3 is statistically non-inferior to the change from Baseline for subjects treated with at 12 weeks after the last treatment as assessed by the BLE using the TLFS. The difference in the TLFS change from Baseline to 12 weeks will be used to establish non-inferiority
Se	condary effectiveness	
•	To assess the effectiveness of RHA® 3 versus and fullness to the lips in subjects seeking lip augmentation up to 52 weeks	 TLFS change from Baseline assessed: By the BLE at Visit 4 and each visit at the study site afterwards
•	To assess the responder rate of RHA® 3 versus augmentation up to 52 weeks	 Responder rate calculated using TLFS assessed: By the BLE at Visit 4 and each visit at the study site afterwards A responder will be defined as a subject who has a ≥1-grade improvement on the TLFS
•	To assess the subject satisfaction and patient-reported outcome of the aesthetic procedure (FACE-Q) with RHA [®] 3 versus Constant of after lip augmentation up to 52 weeks	 Subject satisfaction using the Subject Satisfaction Scale at each visit at the study site starting at Visit 2 FACE-Q scores for each module (satisfaction with lips and satisfaction with outcome) assessed by the subject at each visit at the study site
•	To assess the GAIS of RHA [®] 3 versus Control of Control of Cont	 GAIS as assessed: By the BLE starting at Visit 4 and each visit at the study site afterwards

Table 6-1Objectives Mapped to Endpoints

Page 40 of 132

Page 41 of 132

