10.2.1. Relationship to Device

For each AE identified in the investigation, the TI or designee must assess its relationship to the study and the control device and/or to the procedure. The TI must determine whether there is a reasonable possibility that these caused or contributed to an AE.

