11.3. Subjects and Demographics

11.3.2. Clinical Investigation Plan Deviations

A CIP deviation is any noncompliance with the clinical investigation CIP or International Council for Harmonization of Technical Requirements for Pharmaceuticals for Human Use (ICH) GCP requirements. The noncompliance may be either on the part of the subject, the TI, or study site staff. Corrective actions are to be developed by the site and implemented promptly.

It is the responsibility of the site TI to report any CIP deviations after identification. All deviations must be addressed in study source documents and reported to the sponsor. Clinical investigation plan deviations must be sent to the reviewing IRBs as per local regulations. The site TI is responsible for knowing and adhering to the reviewing IRB requirements. Further details about the handling of CIP deviations will be included in the CIP deviation guidance plan.

Confidential
Clinical Investigation Plan
will be collected
11.4. Effectiveness Analyses Effectiveness analyses will be performed primarily on mITT analysis set.
The primary analysis will be performed as follows: to demonstrate non-inferiority of RHA [®] 3 compared to at 12 weeks after the last treatment; the difference in the change will then be tested between groups (RHA [®] 3 minus

Page 91 of 132

Confider	tial
Clinical Investigation Plan	
Secondary Effectiveness Analysis:	
Secondary analyses will be of descriptive nature	

For the parameters hereafter:

- TLFS: BLE
- Responder rate based on TLFS
- GAIS: BLE,
- FACE-Q scores for each module: Subject (after data standardization, as detailed in SAP)
- Subject satisfaction score: Subject (quantitative scores and categories as described in SAP)

		وجداد والمرا	

For each product, summary statistics (mean, minimum, maximum, SD, and 95% CI of the mean) for the above-mentioned parameters will be provided/presented for each study visit.

For endpoints with qualitative results, frequencies and percentages will be calculated and presented for each study visit.

	Confidential	
Clinical Investigation Plan		
	-	

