#### 9.1. Adverse Events

Adverse events will be recorded either directly by the TI or will come from CTR diary per their duration (

All AEs will be coded using the MedDRA dictionary.

Number of all AEs, ADEs,

All AEs reported during the study will be described by SOC and PT. Incidence rates defined as number of subjects presenting the AE divided by the number of subjects in the treatment group

The causal relationship of the AE to the study treatment is determined by the investigator by relationship to the study procedure and relationship to the study device

Page 38 of 53

The same analyses will be performed for ADEs including also tabulation by SOC and PT.

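### Does the SAP's GAIS text put the secondary endpoint in the hands of the wrong rater?

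*SAP*

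**What the plan says.** The SAP's secondary endpoint list (section 2.2.1.2) gives the GAIS rater as follows: "By the BLE starting at each visit at the study from Visit 4". Protocol Table 6-1 has the matching entry: "By the BLE starting at Visit 4 and each visit at the study site afterwards". The protocol synopsis repeats it, protocol section 8.2.2.3 has the BLE perform the assessment, and the list of secondary parameters in protocol section 11.4 puts the BLE beside GAIS.

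The analysis text in SAP section 8.3 differs. After the responder-rate subsection, and just before the five grades are listed, it states: "The GAIS is a subjective 5-grade dynamic scale as detailed below, will be assessed by Investigators and subjects". The visible plan for GAIS at that point is frequencies and percentages at each study visit.

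Two other statements set the weight of the endpoint. Protocol section 11.4 says: "Secondary analyses will be of descriptive nature". SAP section 8 has a general rule: "For categorical variables, the 2 groups will be compared using independent-testing based on a 2-group, 2-sided, Fisher's exact test". That section also bases the analyses on the mITT population and repeats them in the PP population.

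**The concern.** The raters in this trial are not interchangeable. Protocol section 7.2 leaves the TI unblinded and blinds the BLE and the subjects. If GAIS is recorded by more than one of them, the name of the rater tells the reader whether a table shows a blinded or an unblinded assessment.

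The word *Investigators* is not defined in the visible SAP, and it can be read as the TI. SAP section 9.1 says: "The causal relationship of the AE to the study treatment is determined by the investigator". Protocol section 10.2.1 gives that same task to the TI: "the TI or designee must assess its relationship to the study and the control device and/or to the procedure". By contrast, where SAP section 8.3 deals with lip fullness, its heading names the rater: "TLFS Assessed by BLE". Taken alone, the GAIS sentence could therefore be read as analysing TI and subject ratings in place of the BLE's. An unblinded rating might then be tabulated as the secondary endpoint, or compared between groups under the general rule for categorical variables.

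**Working it through.** There is no figure to recompute: the point involves no margin, variance, error rate or sample size. The check is to compare every visible statement of who rates GAIS.

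| Place | Rater named | Role of the text |
|---|---|---|
| Protocol synopsis, secondary endpoints | BLE, from Visit 4 | Defines the endpoint |
| Protocol Table 6-1 | BLE, from Visit 4 | Defines the endpoint |
| Protocol 8.2.2.3 | BLE, followed by a gap in the text | Describes the assessment |
| Protocol 11.4 | BLE, followed by a trailing comma | Lists parameters for analysis |
| SAP 2.2.1.2 | BLE, from Visit 4 | Defines the endpoint |
| SAP 8.3, GAIS text | Investigators and subjects | Introduces the grade list |

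1. **Which text governs.** Five statements name the BLE and one does not. The three that define the endpoint all name the BLE. The sixth describes the scale before its grades are listed and does not claim to redefine the endpoint. SAP section 1 also makes the protocol the reference document and says that operational details of data collection are not repeated unless the analysis needs them. Read together, the secondary endpoint is the BLE's rating.

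2. **Whether the sentence is false.** This cannot be shown. The gap in protocol section 8.2.2.3 and the comma in section 11.4 are what one would see if further GAIS raters were blacked out after the BLE. Protocol section 7 has the TI make effectiveness evaluations at each study visit, so a TI rating is plausible. The sentence may simply describe who uses the scale.

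3. **What is not visible.** The public SAP runs from 8.3.2 into the GAIS text without showing a heading, and the next visible heading is 8.3.4. The missing heading may name the rater, as the heading of 8.3.1 does. The text after the grade list and the planned table titles are also not visible. The absence of the BLE from one visible sentence does not show that it is absent from the subsection.

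4. **What an analyst would do.** The endpoint definition asks for the BLE's GAIS from Visit 4. The analyst would tabulate that rating by visit. If other ratings are on file, they would get tables of their own. No reading of the SAP as a whole leads to dropping the BLE's GAIS.

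5. **What depends on it.** The primary analysis uses the BLE's lip fullness grade and does not involve GAIS. The protocol treats secondary analyses as descriptive, so a GAIS comparison made under SAP section 8 would not carry a confirmatory claim.

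**The case for a change.** The best case for acting is that *Investigators* is an unnatural word for the BLE. Protocol section 12.1, on investigator responsibilities, describes the TI's duties. In protocol section 9.3.2 investigators and research staff are to withhold the assigned treatment from the subject, whereas the BLE does not know that assignment. The mismatch is also awkward whether or not other raters exist. If several people rate GAIS, the analysis text should say which rating is the endpoint. If only the BLE does, the sentence names raters who supply no data. A one-line clarification would cost almost nothing.

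Much of this stands. The sentence is current text, it does not name the BLE, and the ordinary reading of the word points to the TI. A looser use that covers the BLE cannot be excluded, but it is not the obvious one. What does not stand is the step from loose wording to a wrong analysis. The question of which rating is the endpoint is answered in SAP section 2.2.1.2, and the analysis section need not answer it again. Replacing the rater phrase could also delete a statement that is true. A low cost does not justify an amendment when nothing in the analysis would differ.

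**Conclusion.** The mismatch is a clerical slip, or a general description of the scale that reads oddly in the public copy. It is not a fault in the analysis plan. The secondary GAIS endpoint is the BLE's rating by explicit definition in both documents. The effect on any estimate, interval, test, error rate or sample size is nil.

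This rests on two assumptions: that analysts take the endpoint from the section that defines it, and that tables carry the name of the rater if more than one rating exists. Both are ordinary practice, and nothing visible contradicts them. Confidence that the wording differs is high. Confidence about why it differs is only moderate, because the GAIS heading, the text after the grade list and the planned tables cannot be seen. If the SAP is revised for another reason, naming the BLE in the GAIS text would tidy it, but the plan works without that.
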